Following the two weeks of CREMA data collection, a laboratory session will be conducted to investigate responses to acute dosing of oxytocin (versus placebo) in context of controlled evaluation of stress reactivity and smoking behavior. Prior to the session, participants will abstain from smoking for 12 hours and provide a salivary sample for measurement of stress and sex hormone (cortisol, estradiol, progesterone, and testosterone) levels. Participants will receive a double blind intranasal dose of oxytocin or placebo and will then be exposed to the Trier Social Stress Test (TSST). Measures collected at multiple time points during the laboratory session will include subjective craving, stress, and negative emotion as well as heart rate, blood pressure, skin conductance, and cortisol. Immediately following the TSST, participants will complete a smoking resistance task (SRT) in which they will receive a monetary reward for every 5-min period they can resist smoking. After completing the SRT, participants will be allowed to smoke freely during a one-hour ad libitum smoking period (ASP), with smoking topography assessed via a portable device.

Aim 1: Evaluate gender and sex hormone influences on reactivity to stressful and smoking-related cues presented, via CREMA, in the natural environment of smokers.

Hypothesis 1: Female smokers will be more reactive (craving ratings) than male smokers to stressful and smoking-related cues presented in the natural environment.

Hypothesis 2: Among female smokers, estrogen to progesterone ratio will be positively related to reactivity (craving ratings) to stressful and smoking-related cues presented in the natural environment.

Aim 2: Evaluate gender, sex hormone, and oxytocin administration influences on stress, craving, and smoking behavior response to a laboratory-based stressor task (TSST).

Hypothesis 1: Female smokers will evidence greater subjective stress, craving, and smoking behavior (e.g., shorter latency to smoke during the SRT and greater number of puffs during the ASP), but less neuroendocrine reactivity (cortisol), to the TSST than male smokers.

Hypothesis 2: Oxytocin, relative to placebo, will attenuate subjective stress, craving, and neuroendocrine responses to the TSST.

Hypothesis 3: Among female smokers, estrogen to progesterone ratio will be positively related to craving reactivity during the TSST.

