testosterone in males). On the last day of the second week, following a 12-hour period of smoking abstinence, a laboratory session will be conducted. At the beginning of this session, participants will receive nasal administration of either oxytocin (OXY) or placebo (PBO) prior to the administration of the Trier Social Stress Test (TSST). Random assignment and double-blinding procedures will be employed to ensure that (a) each participant will have an equal probability of receiving OXY or PBO, (b) approximately half of the female and male smokers will receive OXY while the remaining half will receive PBO, and (c) neither the participant nor the research staff will know whether the participant received OXY or PBO. Established self-report, physiological, and laboratory measures of stress/cue reactivity will be administered at regular intervals prior to, during and following the TSST. To assess the acute effects of stress on smoking behavior, the TSST will be followed by a smoking resistance task (SRT) and an ad libitum smoking period (ASP) using smoking topography assessment technology.

We considered several potential alternative designs, including options that would involve only naturalistic or laboratory assessments/procedures (rather than both). The naturalistic (CREMA) approach holds appeal in terms of innovation, and allows for an analytically strategic pairing of cue reactivity and smoking behavior measurement (multiple sessions daily) with serial reproductive hormone measurement over the course of two weeks. The laboratory approach provides assessment of reactivity in a highly structured and controlled environment, and allows for detailed assessment of the acute effects of a standardized stressor on smoking behavior, as assessed with the SRT and ASP. It also permits the assessment of the effects of a very novel pharmacological agent, oxytocin, on stress reactivity and smoking behavior. Therefore, we concluded that the proposed design offers a mutually complementary integration of naturalistic and laboratory-based methodologies that balance internal and external validity and maximize the opportunity to comprehensively assess the role of gender and sex hormones in stress induced alterations in smoking behavior.

C3b. Participants and Recruitment.

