This study is powered to test the hypothesis that non-cigarette-deprived females will be more reactive to smoking cues than males, as measured in the natural environment of smokers via CREMA technology. However, the sample size obtained for this is adequate to test all the four hypotheses with at least 80% power. The justifications for the power calculations are as follows. A recent study (Heishman, et al., 2010) found that non-cigarette-deprived females responded to smoking cues with 10% greater craving than males (i.e., 10-unit difference on a 100-mm VAS), with this difference corresponding to an effect size of $d = 0.7$. Since the proposed design intends to assess gender differences in a non-laboratory setting, we have reduced the expected effect size by 30% to 0.50. Based on the four-item subscale of the QSU (cf., Warthen & [name], 2009b) to be used in the proposed study, a comparable detectable gender difference would be 0.45 ($sd=0.9$). Accounting for the multiple correlated measures within each participant (i.e., reactivity will be measured multiple times daily for 14 days using CREMA) through a between-observation correlation (autocorrelation) of 0.70, a sample of 96 females and 48 males is necessary to achieve 90% power (with a two sided type I error rate of 0.05) to detect the minimum relevant effect size of $d=0.50$. It is estimated that up to 20% of the participants may be lost before completion of the study.

Assuming 144 participants complete all study procedures (accounting for 20% dropout), we will also have 80% power with a type I error of 0.05 to detect a minimum effect size of $d=0.50$ between females and males in stress and craving response to the TSST and similarly between the oxytocin and placebo groups.

C3j. Data Management & Statistical Analysis.

Data Management

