menses. Linear models may thus be inappropriate. Traditional analyses group the hormone curves based on the estimated phases of women's menstrual cycle (follicular and luteal) for the analyses. In addition to performing the data analyses using the same method, analysis will be extended to incorporate the non-linear patterns of an individual's hormone profile. This method will be based on a non-linear regression model that has two to three segments, each one of which may be either quadratic or linear (Marrie, Dawson, & Garland, 2009). The 'joint-points' at which the segments meet, which are referred to as knots, will also be treated as unknown and determined through the modeling process. After identifying the segments, regression models assessing hormone measures against the outcome (e.g., cue-elicited craving) in each segment will be assessed and the results interpreted accordingly.

Aim 2: Hypotheses 1 and 2 - To test for gender and medication (oxytocin versus placebo) effects on reactivity profiles to the TSST during the laboratory session, a linear mixed effects model in which the dependent variables of interest are craving, stress and neuroendocrine (cortisol) response, and the primary independent fixed effects are gender, treatment group, and a random subject effect will be utilized. To account for the repeated measures, a covariance pattern for the error structure (such as an AR(1)) will be considered. The primary goal of this analysis will be to determine if the response to TSST is significantly different between females and males and/or significantly different between those who received oxytocin versus placebo (main effects of gender and medication). Additionally, as a secondary analysis, the interaction between gender and medication condition will be explored.

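### The primary test of Aim 2 Hypothesis 1 averages the female-male difference over oxytocin and placebo recipients; the plan should say so and also report the difference in each arm

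*Combined protocol and SAP*

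**What the plan says.** - **Specific Aims, Aim 2 Hypothesis 1:** "Female smokers will evidence greater subjective stress, craving, and smoking behavior", and less cortisol reactivity, to the TSST than men. No medication condition is mentioned.
- **Specific Aims, Aim 2 Hypothesis 2:** "Oxytocin, relative to placebo, will attenuate subjective stress, craving, and neuroendocrine responses to the TSST".
- **C3a Overview:** "participants will receive nasal administration of either oxytocin (OXY) or placebo (PBO) prior to the administration of the Trier Social Stress Test (TSST"), with allocation such that "approximately half of the female and male smokers will receive OXY while the remaining half will receive PBO".
- **C3j, Aim 2, Hypotheses 1 and 2:** a linear mixed model has gender and treatment group as fixed effects. The primary goal is to learn whether the TSST response differs by gender and/or is "significantly different between those who received oxytocin versus placebo (main effects of gender and medication"). Then, "as a secondary analysis, the interaction between gender and medication condition will be explored". No female-male estimate within an arm is named.
- **C3j, smoking outcomes:** time to smoking in the smoking resistance task (SRT) is compared between the sexes with a complementary log-log or Cox model, and no treatment term is named. No model is given for puffs in the ad libitum smoking period (ASP).
- **C3i:** "a sample of 96 females and 48 males is necessary to achieve 90% power" for Aim 1. The same 144 completers are said to give 80% power to "detect a minimum effect size of $d=0.50$ between females and males in stress and craving response to the TSST", and likewise for oxytocin against placebo. C3i does not say whether 0.50 is the difference without drug or the average over both arms.

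**The concern.** Hypothesis 1 reads as a question about the sexes' own response to a stressor. The test that answers it uses a sample of whom about half have just received a drug expected to dampen that response. Having treatment group in the model removes a shift of the same absolute size in women and men. It does not remove a drug effect that differs between them. Such a difference needs no sex-specific pharmacology: if oxytocin lowers everyone's response by the same fraction, the more reactive sex loses more in absolute terms and the gap narrows in the oxytocin arm. This applies to craving and subjective stress, where women are expected to react more, and to cortisol, where men are.

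At stake is the reading of the result. A small pooled difference could be reported as little gender difference in stress response when the undrugged difference is larger. Under the opposite pattern, a large pooled difference could overstate it. A reader would have no planned drug-free estimate to compare it with.

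**Working it through.** **Inputs.** From C3i: 96 women and 48 men completing, d = 0.50, alpha 0.05. C3i states a two-sided test only for Aim 1; it is assumed here too. From C3a: about 1:1 oxytocin to placebo within each sex, so 48 women and 24 men per arm. The documents give no oxytocin effect by sex, so the drug effects below are assumptions shown as a range. One summary response per person is used, in SD units.

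**Step 1: the plan's own figure.** The standard error (SE) of the pooled gender difference is √(1/96 + 1/48) = 0.177. The noncentrality is 0.50/0.177 = 2.83. Noncentral t, two-sided 0.05, gives power **80.2%**, which matches the plan. A one-sided test would give about 88%, so two-sided is the better fit.

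**Step 2: what the pooled effect estimates.** Suppose the undrugged gap is 0.50 and oxytocin suppresses the more reactive sex by *e* SD more than the other.

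- Gap in the placebo arm: 0.50. Gap in the oxytocin arm: 0.50 − e.
- With 1:1 allocation in each sex, the pooled gap is 0.50 − e/2.
- If both sexes are attenuated by the same fraction *f*, then e = 0.50f and the pooled gap is 0.50(1 − f/2).

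| Assumed oxytocin effect | e | Pooled d | Power, 96 vs 48 |
|---|---|---|---|
| Less reactive sex suppressed 0.25 SD more | −0.25 | 0.625 | 94% |
| Less reactive sex suppressed 0.10 SD more | −0.10 | 0.55 | 87% |
| Equal absolute effect | 0 | 0.50 | 80% |
| Proportional, f = 0.1 | 0.05 | 0.475 | 76% |
| Proportional, f = 0.2 | 0.10 | 0.45 | 72% |
| Proportional, f = 0.3 | 0.15 | 0.425 | 67% |
| Proportional, f = 0.5 | 0.25 | 0.375 | 56% |

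Simulation of the additive model (20,000 runs each) gave mean estimates of 0.62, 0.50 and 0.37 and power of 94%, 81% and 56% for e = −0.25, 0 and 0.25.

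**Step 3: can the secondary interaction test reveal this?** The SE of the difference in gaps is √(2/48 + 2/24) = 0.354. For f = 0.2, 0.3 and 0.5 the interaction is 0.10, 0.15 and 0.25, with power of about 6%, 7% and 11%. A non-significant interaction would therefore not show that the gaps are alike.

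**Step 4: the drug-free contrast.** The placebo arm has 48 women and 24 men. Its SE is √(1/48 + 1/24) = 0.250, which is 0.250/0.177 = 1.4 times the pooled SE. Power at d = 0.50 is 51%.

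**Step 5: accuracy for the undrugged gap under proportional attenuation.** The pooled bias is 0.25f, so its root mean squared error is √(0.177² + (0.25f)²): 0.18 at f = 0.1, 0.18 at 0.2, 0.19 at 0.3 and 0.22 at 0.5. The placebo-arm value is 0.25 throughout. The two are equal when 0.25f = √(0.250² − 0.177²) = 0.177, that is, f about 0.7.

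**The case against.** **The power statement is not wrong.** A reader might infer that the 80% holds only if oxytocin acts equally in women and men. The documents do not support that. C3i names a detectable difference of 0.50 without tying it to undrugged participants, and the figure is right for a difference averaged over arms. Unequal action can also raise power, as the 94% row shows. Even the word equal needs care, because an equal proportional effect still narrows the gap. This objection stands in full.

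**Heterogeneity is assumed.** No section gives a sex-specific or proportional oxytocin effect. The Significance section calls oxytocin relevant to gender, and C1 and C3j plan to explore the interaction, but neither predicts unequal action. In the C1 pilot, craving was lower on oxytocin both before (p = .06) and after (p = .03) the stressor. That fits a general downward shift, which the treatment term would absorb. This stands as to size: the losses above are conditional. It does not settle which difference Hypothesis 1 is about.

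**The plan already has the main parts.** Treatment is in the TSST model, allocation is about even within sex, and the interaction is planned. Main effects first is conventional for two factors. That is a good reason to keep the primary test. It leaves the by-arm estimates unreported and the smoking-outcome models without a named treatment term.

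**A placebo-only test could do worse.** A reader might conclude that all inference on Hypothesis 1 should move to the placebo arm. Steps 4 and 5 argue against that: 51% power, and a larger error than the pooled estimate until attenuation reaches about 70%. This stands.

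**Enrolment is stated two ways.** C3b gives 250 smokers; section 1.1 gives 120 women and 60 men. With 250, 20% loss and an assumed 2:1 split (about 133 and 67), pooled power is about 91% at f = 0, 81% at 0.3 and 70% at 0.5. Power improves, but the proportional understatement, f/2, is unchanged.

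**Conclusion.** The point holds as one of definition and reporting. The primary test of Hypothesis 1 estimates a gender difference averaged over a half-medicated sample, whereas the hypothesis names no drug. The two coincide only if oxytocin's absolute effect is the same in both sexes. Under proportional attenuation of 20% to 50%, the pooled difference understates the undrugged one by 10% to 25%. If the less reactive sex is suppressed more, it overstates it.

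The 80% in C3i is correct for an average difference of 0.50 with 144 completers. For an undrugged difference of 0.50 it could be 67% (f = 0.3), 56% (f = 0.5) or 94% (0.25 SD more suppression in the less reactive sex). These figures rest on assumed oxytocin effects, one summary response per person and two-sided testing. The documents do not show that the design is underpowered for its stated contrast or that the pooled test should be abandoned. The change is inexpensive and worth making.

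**What to change.** 1. **C3j, Aim 2, Hypothesis 1:** keep the pooled gender main effect as the primary test, and describe it as an average over the oxytocin and placebo arms.
2. From the gender-by-medication model already planned, report the female-male difference in the placebo arm and in the oxytocin arm, each with its confidence interval, beside the pooled estimate and the interaction. Do not treat a non-significant interaction as evidence that the arms agree.
3. **C3j, smoking outcomes:** include medication in the models for SRT latency and ASP puffs, and report those outcomes the same way. C1 expects oxytocin to affect them, and leaving a prognostic factor out of a hazard model generally pulls the gender hazard ratio toward the null even when allocation is balanced.
4. **C3i:** state that the 80% refers to the gender difference averaged over arms.
5. Do not substitute a placebo-only test or rest all inference on the placebo arm.

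The cost is analysis-plan wording, with no added participants or measurements. The by-arm estimates are less precise: SE 0.25 against 0.18 SD, or 95% intervals of roughly ±0.49 against ±0.35 SD (1.96 × SE). They should be read as supporting estimates.

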Relevant Oxytocin Experience. Members of MUSC’s SCOR research team ([name], [name]) recently completed a pilot study examining the effects of intranasal oxytocin vs. placebo on the subjective craving and anxiety responses of marijuana-dependent individuals before and after administration of the Trier Social Stressor Task (TSST). Figure 4 depicts the mean craving responses of the oxytocin vs. placebo treated groups prior to receiving oxytocin/placebo (Pre-Med BL), after receiving oxytocin/placebo but prior to the TSST (Post-Med BL) and immediately following the TSST (Post-TSST). The data indicate that while the groups exhibited similar levels of craving prior to medication administration, oxytocin appears to have a dampening effect on craving both before ($p = .06$) and after ($p = .03$) the TSST is administered. Parallel finding were observed for subjective anxiety (not shown). Thus, these preliminary findings suggest that oxytocin may have potential as therapeutic adjunct for managing both basal and stress-elicited craving and anxiety in substance dependent individuals. The proposed project will employ a similar research strategy with nicotine dependent smoker to examine whether oxytocin (vs. placebo) (a) reduces stress and craving reactivity to the TSST, and (b) enhances smoking resistance and attenuates smoking behavior/topography. Since the sex hormone levels of a substantial number of male and female smokers will be quantified in the two-week period preceding the laboratory stress procedures, the proposed research design will permit an exploratory analysis of the association between sex hormone levels and oxytocin’s impact on laboratory measures of stress reactivity/smoking behavior and also the interaction between medication condition and gender.

[figure not shown]
C2. Research Team

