The TSST procedure is widely recognized as the gold standard for evoking stress response in the laboratory (Dickerson & Kemeny, 2004). It begins when the participant is told that (s)he will soon have to perform both a speech and arithmetic task in front of an audience. They are told that the topic of the speech is why (s)he should be hired for a particular job (the participant's "dream job"). The participant will deliver the speech as though speaking to a group of hiring managers. The experimenter then tells the participant that (s)he has 5 min to prepare the speech, and starts the countdown clock (placed in view of the participant). The experimenter leaves the room to allow the participant to prepare. Five minutes later, three individuals unfamiliar to the participant (the audience) enter the room and are seated; the participant is instructed by one audience member (the spokesperson) to stand and begin his/her prepared speech (without notes). The speech is delivered for 5 min; if the participant pauses, (s)he is instructed by the spokesperson to continue. At the end of the speech task, the participant is instructed to serially subtract 13 from 1,022 as quickly and accurately as possible. The mental math recitation continues for 5 min, and at its conclusion, the spokesperson instructs the participant to stop and be seated, and the audience leaves the room. The total time for the TSST procedure is approximately 15 min.

Laboratory Procedure Timeline

TIME	PROCEDURE(S)	MEASUREMENT(S)		
10-10:55 AM	General Assessment & Preparation	CO Assessment; Breathalyzer; UDS; Saliva collection (if not done at home); NWSC; STAI, Mood Form; DDT.		
11:00-11:30 AM	Placement of HR & SC sensors & BP cuff; Baseline 1 Measurements; Snack.	CQ; CREMA Mood & Stress Assessment; NWSC; HR, SC & BP; Cortisol.		
12:00 Noon	Intranasal Administration of Oxytocin or Placebo			
12:30 PM	Baseline 2 Measurements	CQ; CREMA Mood & Stress Assessment; NWSC; HR, SC & BP; Cortisol		
12:45-1:00 PM	Trier Social Stressor Task (TSST)			
1:00 PM	Immediate post-TSST assessment; SRT begins.	CQ; CREMA Mood & Stress Assessment; NWSC; HR, SC & BP; Cortisol; DDT		
1:20 PM	20-minute, post-TSST assessment	*Cortisol & subjective stress (verbal report) will be assessed 20, 40 & 60 min. post-TSST.	*CQ, CREMA Mood & Stress Assessment, NWSC, HR, SC & BP will be assessed when each participant ends SRT and during ASP at 30 and 60 min.	
1:40 PM	40-minute, post-TSST assessment			

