To test the hypothesis that females will have a shorter latency to return to smoking than males, a discrete analog to the Cox proportional hazards model will be used. A complementary log-log model for interval censored survival times will be employed (Allison, 1982; Prentice & Gloeckler, 1978) that will take into account the interval nature of the time frame within which the return to smoking occurs. Also considered will be standard Cox proportional hazards models to compare time to begin smoking. Puff intensity, flow rate, and number of puffs will be assessed using a topography device as participants smoke freely for 1 hour following the smoking resistance task. Longitudinal data analytic methods will be applied to the craving, stress and cortisol data obtained during the laboratory session for all time points before and after the TSST.

Hypothesis 3 - To test the association between the estrogen to progesterone ratio and laboratory stress reactivity in women, a linear model will be developed to assess the relationship between hormones and subsequent stress reactivity. The dependent variables of interest will be the craving, stress and neuroendocrine (cortisol) response to the TSST while the independent variables will include the change in the hormone ratio over the week preceding the lab visit as well as the hormone ratio on the day of the visit. Assumptions such as linearity of the relationship between the hormones and reactivity measures, homoscedasticity, and normality of the error distribution will be assessed and variables will be transformed as necessary.

C3k. Operational Plan and Research Timetable.

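### Read as written, the primary Aim 2 test compares average level across the laboratory session, not the response to the TSST, and includes a pre-dose value in the oxytocin effect

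*Combined protocol and SAP*

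**What the plan says.** In Specific Aims, Aim 2 Hypotheses 1 and 2 concern responses to the TSST: that women and men differ, and that oxytocin attenuates subjective stress, craving and cortisol responses.

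Section C3j (Aim 2, Hypotheses 1 and 2) proposes a linear mixed model for craving, stress and cortisol. The primary fixed effects listed are gender and treatment group, with a random subject effect. The primary goal is to learn whether the response differs between women and men and/or is "significantly different between those who received oxytocin versus placebo (main effects of gender and medication"). The only interaction named is gender by medication, as secondary. A later paragraph applies longitudinal methods to the craving, stress and cortisol data "obtained during the laboratory session for all time points before and after the TSST".

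The Laboratory Procedure Timeline (C3f) shows what those time points are. The 11:00-11:30 AM row reads "Placement of HR & SC sensors & BP cuff; Baseline 1 Measurements; Snack". Dosing is at noon, Baseline 2 at 12:30 PM, the TSST at 12:45-1:00 PM and the immediate post-TSST assessment at 1:00 PM. Cortisol and verbally reported stress follow at 20, 40 and 60 minutes. After 1:00 PM, craving is rated when each participant ends the smoking resistance task and during ad libitum smoking.

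Section C3i claims "80% power with a type I error of 0.05 to detect a minimum effect size of $d=0.50" for both the gender and the oxytocin comparison.

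**The concern.** A group main effect in a repeated-measures model with no group-by-time term estimates the group difference averaged over all time points in the model. Two of those points come before the stressor, and one also comes before the drug.

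For gender, which is not randomised, a difference that existed before the stressor would count towards a difference in TSST response. For oxytocin, the drug cannot act at Baseline 1, so including that value pulls the estimate towards zero. The average also cannot separate a drug effect on resting state from an effect on the stress response.

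This is the study's only randomised comparison, and the power statement assumes that the full 0.50 SD is the quantity tested.

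**Working it through.** **Inputs from the documents (C3i unless noted).** Completers: "Assuming 144 participants complete all study procedures (accounting for 20% dropout"). Gender split: "a sample of 96 females and 48 males is necessary to achieve 90% power". Allocation is about half and half (C3a), so 72 vs 72. Effect size is 0.50. Alpha is 0.05, and two-sided is carried over from the CREMA calculation ("with a two sided type I error rate of 0.05").

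**Assumptions.** No laboratory correlation is given; 0.70 is stated for CREMA only. I use ρ = 0.5, 0.7 and 0.8 with compound symmetry and equal weight per time point. The pattern of drug effect over time is also assumed, so two patterns are shown.

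**Formula.** Noncentrality = (Δ/s) × √(n₁n₂/(n₁+n₂)), referred to t on 142 df. The root is √36 = 6 for 72 vs 72 and √32 = 5.657 for 96 vs 48.

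**Step 1: the plan's figure.** One value per person, s = 1:
- Gender: 0.5 × 5.657 = 2.83, power 80.2%. The stated 80% reproduces.
- Oxytocin: 0.5 × 6 = 3.00, power 84.6%. The stated 80% is conservative.
- Enrolment: 144/0.8 = 180, which matches the 120 women and 60 men in section 1.1.

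**Step 2: oxytocin main effect.** The mean of T time points has s = √(ρ + (1−ρ)/T). If the drug acts at k of them, Δ = 0.5 × k/T.
- T = 6 (cortisol; stress if the verbal reports are included): post-stressor only, k = 4, Δ = 0.333; constant after dosing, k = 5, Δ = 0.417.
- T = 3 (Baseline 1, Baseline 2, 1:00 PM): post-stressor only, k = 1, Δ = 0.167; constant after dosing, k = 2, Δ = 0.333.

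| ρ | s, T=6 | post-stressor only | constant | s, T=3 | post-stressor only | constant |
|---|---|---|---|---|---|---|
| 0.5 | 0.764 | 2.62 → 74% | 3.27 → 90% | 0.816 | 1.22 → 23% | 2.45 → 68% |
| 0.7 | 0.866 | 2.31 → 63% | 2.89 → 82% | 0.894 | 1.12 → 20% | 2.24 → 60% |
| 0.8 | 0.913 | 2.19 → 59% | 2.74 → 78% | 0.931 | 1.07 → 19% | 2.15 → 57% |

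In the constant pattern, the true drug effect on the change from Baseline 2 to after the stressor is zero. The six-point main effect is still significant 78% to 90% of the time.

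**Step 3: gender main effect with no difference in reactivity.** Suppose a hypothetical 0.5 SD difference at all six points, so the true difference in change is 0. Noncentrality is 0.5 × 5.657/s = 3.70, 3.27 and 3.10 for ρ = 0.5, 0.7 and 0.8. The test rejects 96%, 90% and 87% of the time.

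**Step 4: the alternatives.**
- Oxytocin at 1:00 PM adjusted for Baseline 1: residual variance 1 − ρ² = 0.75, 0.51, 0.36, so s = 0.866, 0.714, 0.600. Noncentrality 3.46, 4.20, 5.00; power 93%, 99% and above 99%. If Baseline 1 carried no information, power would fall to the 84.6% of Step 1.
- Gender difference of 0.5 SD in the change from Baseline 2 to 1:00 PM: s = √(2(1−ρ)) = 1.000, 0.775, 0.632. Noncentrality 2.83, 3.65, 4.47; power 80%, 95% and 99%.

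**The case against.** The main-effects paragraph lists no time points. It calls the outcome a response, speaks of reactivity profiles, and names only the primary fixed effects, so it is silent on time rather than excluding it. In C1 the same team computed cue reactivity as post-cue minus pre-cue craving. C3j also allows covariates chosen from baseline imbalance checks.

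This has weight. If change from the last pre-stressor value was meant, most of the objection goes. But no change score is defined for the laboratory session, and the later paragraph takes in all time points. An imbalance check for confounders does not prespecify adjustment for the pre-dose outcome. The choice of baseline also matters: in the pilot (C1), "oxytocin appears to have a dampening effect on craving both before" (p = .06) and after (p = .03) the TSST. Change from Baseline 2 would subtract any effect already present at that point.

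A reader might infer that oxytocin power always falls below 80%. The documents do not support that. With six points and a constant post-dose effect it is 82% at ρ = 0.7 and 90% at ρ = 0.5, and the pilot makes an effect before the stressor plausible. Enrolment matters too. C3b gives 250 smokers, so 200 completers after 20% loss, or 100 vs 100. The root becomes √50 = 7.07, and the post-stressor-only pattern then gives 0.333 × 7.07/s = 3.09, 2.72 and 2.58, or 87%, 77% and 73%.

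A reader might also fault AR(1) because the assessments are unequally spaced. The text offers it only as an example to be considered, so no error is fixed in the plan.

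Finally, the study is sized on Aim 1, and the section on the importance of the knowledge describes oxytocin work as exploration. Aim 2 nevertheless states a directional oxytocin hypothesis, and C3i claims power for it.

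**Conclusion.** The concern stands for the text as written. The primary Aim 2 test does not isolate the response to the TSST, for either gender or oxytocin. That problem of what is estimated does not depend on the correlation.

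Its size does. A purely tonic gender difference of 0.5 SD, which is hypothetical, would be taken for a TSST response 87% to 96% of the time. Oxytocin power ranges from 59% to 90% over six points and from 19% to 68% over three, against a stated 80%. Whether it falls short depends on when the drug effect appears, how many time points enter and how many participants complete. These figures rest on 144 completers, compound symmetry, equal weighting and an assumed laboratory correlation of 0.5 to 0.8.

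**What to change.** In C3j, Aim 2:

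- Include time as a categorical factor and list the time points used for each outcome.
- **Oxytocin:** make the primary estimate the treatment difference at the immediate post-TSST (1:00 PM) assessment, adjusted for the pre-dose Baseline 1 value and gender. Report the Baseline 2 difference separately, as a drug effect before the stressor.
- **Gender:** test the gender-by-time contrast, 1:00 PM minus Baseline 2, adjusted for treatment.
- Name any later cortisol or verbal-stress points as secondary. The smoking resistance task begins at 1:00 PM and participants may smoke at any time from then, so an average over later points would mix the TSST response with smoking.
- Restate the C3i power claim for these contrasts, with the assumed correlation.

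All the data are already collected, so only wording changes. Section 5.9 places the unblinded analysis after all participants have completed, so the change can be fixed before then. The cost is small: later time points carry less weight in the primary test, so a response still developing at 1:00 PM would appear mainly in the secondary analyses. The gender contrast would have less than 80% power for 0.5 SD if the laboratory correlation were below about 0.5.
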